7.1.2.7 Target/Non-Target Lesions

All measurable lesions, up to a maximum of 2 per organ and 5 in total, should be identified as target lesions to be measured and recorded at baseline. The target lesions should be representative of all involved organs. Target lesions will be selected based on their size (the lesion with the longest diameter) and suitability for accurate repeated measurements. At baseline, a sum of the longest diameters for all target lesions will be calculated and recorded as the baseline tumor burden. The baseline sum will be used as the reference point to determine the objective tumor response of the target lesions.

Measurable lesions other than the target lesions and all sites of non-measurable disease will be identified as non-target lesions and will be recorded at baseline. Non-target lesions will be evaluated at the same time points as target lesions.

7.1.2.8 Response in Measureable Lesions (RECIST 1.1)

At baseline, the sum of the longest diameters (SumD) of all target lesions (up to 2 lesions per organ, up to total 5 lesions) is measured. At each subsequent tumor assessment, the SumD of the target lesions and of new, measurable lesions (≥ 10 mm; up to 2 new lesions per organ,

total 5 new lesions) are added together to provide the total measurable tumor burden (TMTB):

$$\text{TMTB} = \text{SumD target lesions} + \text{SumD new, measurable lesions}$$

Percentage changes in TMTB per assessment time point describe the size and growth kinetics of both old and new measurable lesions as they appear. At each tumor assessment, the response in target and new measurable lesions is defined based on the change in TMTB.

- Complete Response (CR): Disappearance of all target lesions. Any pathological lymph nodes (whether target or non-target) must have reduction in short axis to <10 mm.
- Partial Response (PR): At least a 30% decrease in the sum of diameters of target lesions, taking as reference the baseline sum diameters.
- Progressive Disease (PD): At least a 20% increase in the sum of diameters of target lesions, taking as reference the smallest sum on study (this includes the baseline sum if that is the smallest on study). In addition to the relative increase of 20%, the sum must also demonstrate an absolute increase of at least 5 mm. (Note: the appearance of one or more new lesions is also considered progression).
- Stable Disease (SD): Neither sufficient shrinkage to qualify for PR nor sufficient increase to qualify for PD, taking as reference the smallest sum diameters while on study.

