7.1.2.6 Measurable and Non-measurable Lesions and Disease

Measurable lesions will be those that can be accurately measured in at least one dimension with the longest diameter ≥ 10 mm (for spiral CT scan or MRI scan, ≥ 5 mm). Measurable disease will be present if the subject has 1 or more measurable lesions.

Non-measurable lesions/disease will be all other lesions (or sites of disease), including small lesions (those with all measurements <10 mm or <5 mm with spiral CT/MRI), or any of the following: bone lesions, leptomeningeal disease, ascites, pleural or pericardial effusion, lymphangitis, cutis/pulmonis, abdominal masses that are not confirmed and followed by imaging techniques, cystic lesions, and lesions occurring within a previously irradiated area unless they are documented as new lesions since the completion of radiation therapy.

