7.1.2.9 Immune-Related Response in Measureable Lesions (irRECIST)

In addition to evaluation using RECIST 1.1 criteria, an immune response adaptation of RECIST will be applied to this trial. The essential differences between irRECIST and RECIST criteria are as follows:

New measureable lesions do not necessarily constitute progressive disease and they should be added into the total tumor burden. New non-measurable lesions do not constitute disease progression but will prevent the determination of an irCR.

Apparent disease progression should be confirmed after 4 weeks in the absence of symptoms consistent with clinical deterioration.

At baseline, the sum of the longest diameters (SumD) of all target lesions (2 per organ and 5 in total) is measured. At each subsequent tumor assessment, the SumD of the target lesions and of new, measurable lesions (≥ 10 mm [lymph nodes ≥ 15 mm in shortest diameter]; up to 2 new lesions per organ, total 5 new lesions) are added together to provide the total measurable tumor burden (TMTB):

$$\text{TMTB} = \text{SumD target lesions} + \text{SumD new, measurable lesions}$$

Percentage changes in TMTB per assessment time point describe the size and growth kinetics of both old and new measurable lesions as they appear. At each tumor assessment, the response in target and new measurable lesions is defined based on the change in TMTB (after ruling out irPD) as follows:

- Complete Response (irCR): complete disappearance of all target and new, measurable lesions, with the exceptions of lymph nodes which must decrease to <10 mm in short axis
- Partial Response (irPR): decrease in TMTB $\geq 30\%$ relative to baseline (see below)
- Stable Disease (irSD): not meeting criteria for irCR or irPR, in absence of irPD
- Progressive Disease (irPD): increase in TMTB $\geq 20\%$ relative to nadir

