7.1.2.12 Overall Response

Overall response will be determined based on RECIST 1.1 criteria and by irRECIST criteria (Table 1). Overall response according to irRECIST is derived from the responses in measurable lesions (based on TMTB) and the presence of any non-measurable lesions.

Table 6 Tumor Response Evaluation: Comparison of RECIST 1.1 and irRECIST

Criteria	RECIST1.1	irRECIST
New measurable lesions (≥ 10 mm)	Always represents PD	Incorporated into tumor burden
New non-measurable lesions (< 10 mm)	Always represents PD	Does not define progression but precludes irCR
Non-Target lesions	Changes contribute to defining BOR of CR, PR, SD, and PD	Contribute to defining irCR (complete disappearance required)
CR	Disappearance of all lesions	Disappearance of all lesions
PR	$\geq 30\%$ decrease in the sum of the longest diameter of all target lesions compared with baseline, in absence of new lesions or unequivocal progression of non-target lesions	$\geq 30\%$ decrease in tumor burden compared with baseline
SD	Neither sufficient shrinkage to qualify for PR nor sufficient increase to qualify for PD, taking as reference the smallest sum diameters while on study	Neither a 30% decrease in tumor burden compared with baseline nor a 20% increase compared with nadir can be established
PD	At least 20% increase in sum of diameters of target lesions, taking as reference the smallest sum on study. In addition to the relative increase of 20%, the sum must also demonstrate an absolute increase of at least 5mm. The appearance of one or more new lesions is also considered progression.	At least 20% increase in tumor burden compared with nadir (at any single time point) ^a

irRECIST = immune-related Response Evaluation Criteria in Solid Tumors; BOR = best overall response; CR = complete response; irCR = immune-related complete response; PD = progressive disease; PR = partial response; SD = stable disease;

^a Patients with an initial finding of progressive disease (irPD) before or at the 9-week imaging assessment, but without rapid clinical deterioration, require confirmation of irPD with a second, consecutive scan obtained ≥ 4 weeks from the initiation documentation. Patients will continue to receive study treatment until irPD is confirmed at this later time point. Best overall response (BOR) will therefore include responses occurring at any time before disease progression and after early progression (i.e., within the first 8 weeks of the study).

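### Lymph nodes enter the tumour sum by longest diameter but are judged normal on short axis, so a normalised node can block a partial response and a growing node can be PD on one axis and SD on the other

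*Combined protocol and SAP*

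**What the plan says.** **The sum uses the longest diameter.** Section 7.1.2.7 states that "a sum of the longest diameters for all target lesions will be calculated and recorded as the baseline tumor burden". Sections 7.1.2.8 and 7.1.2.9 both define SumD as "the sum of the longest diameters (SumD) of all target lesions", and Table 6 defines RECIST 1.1 PR as a "decrease in the sum of the longest diameter of all target lesions compared with baseline". None of these makes an exception for nodes. Section 7.1.2.6 defines a measurable lesion as one that can be "accurately measured in at least one dimension with the longest diameter" at or above a cut-off, again without a nodal rule.

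**Nodal status uses the short axis.** For RECIST 1.1 CR, Section 7.1.2.8 says: "Any pathological lymph nodes (whether target or non-target) must have reduction in short axis to <10 mm". Section 7.1.2.10 applies the same 10 mm limit to non-target nodes. For irCR, Section 7.1.2.9 requires disappearance of lesions "with the exceptions of lymph nodes which must decrease to <10 mm in short axis". The same section counts new nodes as measurable only if they are "lymph nodes ≥ 15 mm in shortest diameter".

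**The 15 mm nodal condition appears once.** Section 7.1.2.11, the irRECIST column of Table 6 and the Table 8 footnote give 10 mm without it.

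Section 13.3 says RECIST 1.1 will be used. It does not say how that relates to the rules written out in Section 7, or which prevails if they differ.

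**The concern.** One axis decides whether a node has normalised. The other decides whether the subject has PR, PD, irPR or irPD. The two need not move together: a node can become thin while staying long, or lengthen while its short axis hardly changes. The sum can then disagree with the protocol's own judgement of the node.

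Tumour response and PFS by RECIST 1.1 and irRECIST are primary objectives of Part B (Section 3.4). The trial is open label (Section 5.2.3). The only central review in the visible text is for exploratory volumetric analysis (Section 13.3). An assessor who notices the mismatch has no instruction on how to resolve it, and different assessors may resolve it differently.

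**Working it through.** The plan states no figure on this point, so there is nothing to reproduce. The check applies the protocol's cut-offs to example lesions.

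**Inputs from the protocol**
- PR: a fall of at least 30% from baseline (7.1.2.8); irPR: the same percentage (7.1.2.9).
- PD: a rise of at least 20% from the smallest sum and at least 5 mm (7.1.2.8). irPD: a rise of at least 20% from nadir (7.1.2.9).
- Nodal CR and irCR: short axis below 10 mm.
- New node measurable under irRECIST: shortest diameter at least 15 mm.

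**Assumptions.** Lesion sizes are illustrative, written as long x short axis in mm. Non-target disease does not progress, and there are no new lesions except in case D.

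**Formula.** Change = 100 x (sum now - reference sum) / reference sum.

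**Case A: a normal node blocks PR.** Node 20x15 plus lung lesion 20; later, node 16x8 (below 10, so normal) and lung 14.
- Longest diameters: 20 + 20 = 40 to 16 + 14 = 30. Change = -10/40 = -25.0%: SD.
- Node on short axis: 15 + 20 = 35 to 8 + 14 = 22. Change = -13/35 = -37.1%: PR.

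irPR uses the same sum and cut-off, so the result is the same there.

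**Case B: growth of an existing node.** Sole target node, 20x15 at nadir, then 25x17.
- Longest diameter: +5/20 = +25.0%, and +5 mm: PD and irPD.
- Short axis: +2/15 = +13.3%, and +2 mm: SD and irSD.

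No new lesion is needed, so this case reaches RECIST 1.1 progression and hence PFS.

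**Case C: SD and CR together.** Sole target node 24x16 to 18x9.
- Longest diameter: -6/24 = -25.0%: SD by the sum.
- Short axis 9 mm: CR by the nodal rule.

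The RECIST 1.1 wording of SD does not exclude CR, so both labels fit. Read CR first and the subject is a CR, which is also the result after any change of axis.

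**Case D: a new node, irRECIST only.** New node 22x15 added to a nadir of 100, other lesions unchanged.
- If the nadir contains no nodes: 22/100 = +22% (irPD) by longest diameter; 15/100 = +15% (not irPD) by short axis.
- If the nadir is entirely nodes of the same shape, its short-axis value is 100 x 15/22 = 68.2, and 15/68.2 = +22%: irPD on both axes.

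**Does changing the axis suffice?** No. A target node going from 12 to 9 mm in short axis changes by -3/12 = -25%, which is still SD by the sum and CR by the nodal rule. With a baseline minimum of 15 mm, n target nodes start at 15n or more and, once all are below 10, end below 10n. The fall exceeds 5/15 = 33.3%, so a node-only CR always clears the 30% cut.

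**Scale of one subject.** Forty-eight Part B subjects at 1:1:2 give arms of 12, 12 and 24. One reclassified responder is 1/12 = 8.3 or 1/24 = 4.2 percentage points. This is the weight of one subject, not an estimate of bias.

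**The case against.** **The text is consistent if read literally.** SumD is a longest-diameter sum throughout, and qualifying a lesion on one measure while summing another could be a design choice. This stands for the label in cases B and D: the written rule gives one answer. It does not remove case A, where following the rule literally withholds PR because of a node that the protocol itself calls normal.

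**Section 13.3 adopts RECIST 1.1.** What that standard says about nodal axes cannot be checked from these documents. Section 7 sets out its own operative rules, and nothing states which text governs.

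**A reader might infer that the SD/CR overlap changes the response rate.** It does not. CR is not defined by the sum, Table 7 takes target CR with non-target CR and no new lesions to overall CR, and irSD expressly excludes irCR. The overlap is confined to the RECIST 1.1 wording of SD, and reading CR first resolves it.

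**A reader might infer that new nodes are generally overweighted towards progression.** The documents do not support that. Under RECIST 1.1 any new lesion is PD whatever its size. Under irRECIST the result depends on the mix of nodal and non-nodal lesions in the nadir, as case D shows. The last row of Table 8 may also make an unequivocal new lesion irPD regardless of the sum. In addition, irRECIST is applied secondarily in the analysis text (Sections 2.2 and 8.1), and apparent progression is to be confirmed after 4 weeks in the absence of clinical deterioration.

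**The same rule applies in all arms, and comparisons are made only as a reference.** That is true. It limits the consequence for between-arm testing, but not for the response rate and PFS reported within each arm.

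**Conclusion.** The point holds for existing nodes. As written, the rule can withhold PR from a subject whose node has normalised (-25% against -37%), and it makes progression of a nodal lesion depend on the axis (+25% and +5 mm against +13%). Both examples bear on primary objectives of Part B and rest on illustrative sizes.

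The net effect on response rate or PFS cannot be computed. The documents give no proportion of subjects with nodal target disease; that such disease will occur is an assumption. Nor do they settle a direction: the long axis delayed response in one example and brought progression forward in the other, and other node shapes could act differently. The new-node case is secondary and confined to irRECIST. The SD/CR overlap needs a clarifying sentence only. The amendment is worth making because it is cheap and the affected measures are primary.

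**What to change.** - **Sum.** In 7.1.2.7, 7.1.2.8, 7.1.2.9 and Table 6, define SumD and TMTB as longest diameter for non-nodal lesions and short axis for nodal lesions, at baseline, nadir and every visit.
- **Target nodes.** In 7.1.2.6 and 7.1.2.7, set a baseline short-axis minimum for target nodes, consistent with the 15 mm already in 7.1.2.9. Without it, the axis change leaves the 12 to 9 mm case unresolved.
- **New nodes.** Carry the 15 mm condition into the irRECIST texts that omit it: 7.1.2.11, the irRECIST column of Table 6 and the Table 8 footnote. Leave it out of 7.1.2.8, where any new lesion is PD and the condition would change no result.
- **CR.** State that a CR may have a non-zero sum when nodes remain visible below 10 mm, and that CR takes precedence over SD.
- **Data.** Record the nodal short axis on the lesion CRF.

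**Cost.** Protocol wording and one CRF field. The short axis must already be read to apply the CR rule, so no extra scans are needed. Nodes below the minimum become non-target lesions. A subject whose only measurable lesions are such nodes would then have no target lesion, so the sponsor should check the change against inclusion criterion 5, which requires measurable disease.

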7.1.2.9 Immune-Related Response in Measureable Lesions (irRECIST)

In addition to evaluation using RECIST 1.1 criteria, an immune response adaptation of RECIST will be applied to this trial. The essential differences between irRECIST and RECIST criteria are as follows:

New measureable lesions do not necessarily constitute progressive disease and they should be added into the total tumor burden. New non-measurable lesions do not constitute disease progression but will prevent the determination of an irCR.

Apparent disease progression should be confirmed after 4 weeks in the absence of symptoms consistent with clinical deterioration.

At baseline, the sum of the longest diameters (SumD) of all target lesions (2 per organ and 5 in total) is measured. At each subsequent tumor assessment, the SumD of the target lesions and of new, measurable lesions (≥ 10 mm [lymph nodes ≥ 15 mm in shortest diameter]; up to 2 new lesions per organ, total 5 new lesions) are added together to provide the total measurable tumor burden (TMTB):

$$\text{TMTB} = \text{SumD target lesions} + \text{SumD new, measurable lesions}$$

Percentage changes in TMTB per assessment time point describe the size and growth kinetics of both old and new measurable lesions as they appear. At each tumor assessment, the response in target and new measurable lesions is defined based on the change in TMTB (after ruling out irPD) as follows:

- Complete Response (irCR): complete disappearance of all target and new, measurable lesions, with the exceptions of lymph nodes which must decrease to <10 mm in short axis
- Partial Response (irPR): decrease in TMTB $\geq 30\%$ relative to baseline (see below)
- Stable Disease (irSD): not meeting criteria for irCR or irPR, in absence of irPD
- Progressive Disease (irPD): increase in TMTB $\geq 20\%$ relative to nadir

7.1.2.10 Response in Non-measurable Lesions (RECIST 1.1)

While some non-target lesions may actually be measurable, they need not be measured and instead should be assessed only qualitatively.

- **Complete Response (CR)**: Disappearance of all non-target lesions and normalization of tumor marker level. All lymph nodes must be non-pathological in size (<10 mm short axis).
- **Non-CR/Non-PD**: Persistence of one or more non-target lesion(s) and/or maintenance of tumor marker level above the normal limits.
- **Progressive Disease (PD)**: Unequivocal progression of existing non-target lesions. (Note: the appearance of one or more new lesions is also considered progression).

When the patient also has measurable disease, to achieve ‘unequivocal progression’ on the basis of non-target disease, there must be an overall level of substantial worsening in non-

target disease such that, even in presence of SD or PR in target disease, the overall tumor burden has increased sufficiently to merit discontinuation of therapy.

In the event that the patient has only non-measurable disease, the same general concepts apply as noted above, however, in this instance there is no measurable disease assessment to factor into the interpretation of an increase in non-measurable disease burden. Because worsening in non-target disease cannot be easily quantified, a useful test that can be applied when assessing subjects for unequivocal progression is to consider if the increase in overall disease burden based on the change in non-measurable disease is comparable in magnitude to the increase that would be required to declare PD for measurable disease (i.e., an increase in tumor burden representing an additional 73% increase in ‘volume’ which is equivalent to a 20% increase diameter in a measurable lesion).

7.1.2.11 Immune-Related Response in Non-measurable Lesions (irRECIST)

At each tumor assessment, the presence of any new, non-measurable lesions is assessed. The presence of such lesions will rule out an overall response of irCR. An increase in the size or number of new, non-measurable lesions does not necessarily imply an overall response of irPD; if these lesions become measurable (≥ 10 mm) at a subsequent tumor assessment, their measurement will at that point start to contribute to the TMTB.

In addition, the response in non-target lesions is defined as follows:

- Complete Response (irCR): complete disappearance of all non-target lesions
- Stable Disease (irSD): non-target lesions are stable
- Progressive Disease (irPD): unequivocal increases in number or size of non-target lesions. To achieve unequivocal progression of non-target lesions, there must be an overall level of substantial worsening of non-target disease that is of a magnitude that the treating physician would feel it is important to change therapy.

NOTE: Equivocal findings of progression of non-target lesions (e.g., small and uncertain new lesions; cystic changes or necrosis in existing lesions) should be considered irSD, and treatment may continue until the next scheduled assessment.

7.1.2.12 Overall Response

Overall response will be determined based on RECIST 1.1 criteria and by irRECIST criteria (Table 1). Overall response according to irRECIST is derived from the responses in measurable lesions (based on TMTB) and the presence of any non-measurable lesions.

Table 6 Tumor Response Evaluation: Comparison of RECIST 1.1 and irRECIST

Criteria	RECIST1.1	irRECIST
New measurable lesions (≥ 10 mm)	Always represents PD	Incorporated into tumor burden
New non-measurable lesions (< 10 mm)	Always represents PD	Does not define progression but precludes irCR
Non-Target lesions	Changes contribute to defining BOR of CR, PR, SD, and PD	Contribute to defining irCR (complete disappearance required)
CR	Disappearance of all lesions	Disappearance of all lesions
PR	$\geq 30\%$ decrease in the sum of the longest diameter of all target lesions compared with baseline, in absence of new lesions or unequivocal progression of non-target lesions	$\geq 30\%$ decrease in tumor burden compared with baseline
SD	Neither sufficient shrinkage to qualify for PR nor sufficient increase to qualify for PD, taking as reference the smallest sum diameters while on study	Neither a 30% decrease in tumor burden compared with baseline nor a 20% increase compared with nadir can be established
PD	At least 20% increase in sum of diameters of target lesions, taking as reference the smallest sum on study. In addition to the relative increase of 20%, the sum must also demonstrate an absolute increase of at least 5mm. The appearance of one or more new lesions is also considered progression.	At least 20% increase in tumor burden compared with nadir (at any single time point) ^a

irRECIST = immune-related Response Evaluation Criteria in Solid Tumors; BOR = best overall response; CR = complete response; irCR = immune-related complete response; PD = progressive disease; PR = partial response; SD = stable disease;

^a Patients with an initial finding of progressive disease (irPD) before or at the 9-week imaging assessment, but without rapid clinical deterioration, require confirmation of irPD with a second, consecutive scan obtained ≥ 4 weeks from the initiation documentation. Patients will continue to receive study treatment until irPD is confirmed at this later time point. Best overall response (BOR) will therefore include responses occurring at any time before disease progression and after early progression (i.e., within the first 8 weeks of the study).

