7.1.2.5 Tumor Imaging and Assessment of Disease

Computed tomography (CT) and magnetic resonance imaging (MRI) will be considered the best currently available and reproducible methods to measure target lesions selected for response assessment. Conventional CT should be performed with contiguous cuts of 10 mm or less. Spiral CT scan should be performed using a 5 mm contiguous reconstruction algorithm (as a general rule, lesion diameter should be no less than double the slice thickness). Lesions on chest x-rays will be acceptable as measurable lesions when they are clearly defined and surrounded by aerated lung; however, CT is preferable. Ultrasound is not an acceptable method to measure disease.

Assessment of disease will be done using both RECIST 1.1 criteria and irRECIST criteria.

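### Below a nadir sum of 25 mm, irPD has a lower size threshold than RECIST 1.1 PD, because only RECIST 1.1 carries the 5 mm minimum

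*Combined protocol and SAP*

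**What the plan says.** Section 7.1.2.8 gives RECIST 1.1 progression two size conditions, a 20% rise over the smallest sum and a minimum in millimetres: "In addition to the relative increase of 20%, the sum must also demonstrate an absolute increase of at least 5 mm". The RECIST 1.1 column of Table 6 repeats the minimum: "the sum must also demonstrate an absolute increase of at least 5mm".

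The irRECIST definitions carry only the percentage. Section 7.1.2.9 has "Progressive Disease (irPD): increase in TMTB $\geq 20\%$ relative to nadir", where TMTB is the sum of target and new measurable lesions. Table 6 has "At least 20% increase in tumor burden compared with nadir (at any single time point"). The irRECIST SD cell of Table 6 also uses a bare 20% over nadir. No other section gives irPD an absolute minimum.

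Section 7.1.2.9 introduces its comparison with "The essential differences between irRECIST and RECIST criteria are as follows" and names two matters: new lesions, which do not by themselves count as progression, and confirmation of apparent progression after 4 weeks. A different growth threshold is not mentioned. Under RECIST 1.1 a new measurable lesion "Always represents PD" (Table 6).

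Section 7.1.2.12.2 states that irPD at or after Week 9 rules out a later irCR, irPR or irSD as best response. Section 3.4 names irRECIST response and PFS beside RECIST 1.1 in a Part B primary objective. Section 8.1 calls the irRECIST evaluation secondary.

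**The concern.** Both differences listed in section 7.1.2.9 make irRECIST slower to call progression. The missing 5 mm minimum works the other way for small tumour sums, and the plan gives no reason for it.

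The irRECIST endpoints are at stake. A subject whose small sum grows by 20% or more but by less than 5 mm has an irRECIST PFS event, and an irRECIST response ends, while under RECIST 1.1 the subject is stable or still responding. A late response can also be lost from irBOR if the small rise occurs at or after Week 9. A comparison of the two sets of results would then mix the effect irRECIST is meant to show (new lesions, early apparent progression) with an unstated difference in threshold. In Part B, 48 subjects at 1:1:2 give arms of about 12, 12 and 24, so one reclassified subject in an arm of 12 moves a rate by 1/12 = 8.3 percentage points.

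**Working it through.** The plan states no figure of its own on this point, so there is nothing to reproduce. The thresholds follow from its definitions.

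**Thresholds.** Let n be the nadir sum in mm. irPD needs growth of 0.20n (7.1.2.9, Table 6). RECIST 1.1 PD needs growth of max(0.20n, 5) (7.1.2.8, Table 6). They are equal when 0.20n = 5, that is n = 25. Below that the gap is 5 − 0.20n.

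| Nadir (mm) | Growth for irPD | Growth for RECIST 1.1 PD | Gap |
|---|---|---|---|
| 10 | 2.0 | 5 | 3.0 |
| 12 | 2.4 | 5 | 2.6 |
| 15 | 3.0 | 5 | 2.0 |
| 20 | 4.0 | 5 | 1.0 |
| 25 | 5.0 | 5 | 0 |

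**Who reaches a nadir below 25 mm.** From baseline b the shrinkage needed is more than 1 − 25/b: 50% from 50 mm, 66.7% from 75 mm, 75% from 100 mm. A 30% shrinkage is enough only if b is below 25/0.7 = 35.7 mm. One measurable lesion suffices for measurable disease (7.1.2.6), so a baseline of 10 to 24 mm is already in the range with no shrinkage.

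**Two illustrations** (no new lesion, non-target disease stable, irPD counted without a cancelling confirmation scan).

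- Baseline 50 mm, nadir 12 mm, then 15 mm. Growth is 3 mm, or 3/12 = 25%. RECIST 1.1: still PR, since 15/50 is a 70% decrease. irRECIST: irPD, so PFS and duration of response end.
- Baseline 15 mm, 15 mm at Week 9, 18 mm at Week 17, then 10 mm. Growth at Week 17 is 3 mm, or 20%. RECIST 1.1: SD, then PR (5/15 = 33% decrease). irRECIST: irPD at Week 17, after which 7.1.2.12.2 excludes the irPR.

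**Measurement error alone.** Assume the sum is truly unchanged and the difference between two scans is normal with SD 2 mm. The documents give no SD. The chance of crossing at one scan is 1 − Φ(threshold/SD):

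- nadir 10 mm: 1 − Φ(1.0) = 16%
- 12 mm: 1 − Φ(1.2) = 12%
- 15 mm: 1 − Φ(1.5) = 7%
- 20 mm: 1 − Φ(2.0) = 2%
- with the 5 mm minimum: 1 − Φ(2.5) = 0.6%

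At nadir 12 mm, an SD of 1.5 to 3 mm gives 5% to 21% without the minimum and 0.04% to 4.8% with it. If a second crossing is required, and the two differences share the nadir scan (correlation 0.5, equal scan error), the SD of 2 mm gives 6.3%, 4.0%, 1.8% and 0.4% at 10, 12, 15 and 20 mm.

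**How many subjects.** The documents give neither baseline sums nor response rates, so this rests on a simulation with assumed inputs:

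- baseline sums log-normal, median 25 to 90 mm, log-scale SD 0.6, at least 10 mm;
- response in 10% to 40%, with responder shrinkage uniform from 30% to nearly 100%;
- 40% of non-responders shrinking by up to 30%, the rest not at all;
- growth over one scan interval exponential with mean 35% of baseline;
- a new lesion in half of subjects.

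irPD alone was met at that scan in about 0.3% to 8% of subjects. Of 48, that is roughly 0.1 to 4. Responders made up 26% to 95% of those cases.

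**The case against.** The bare 20% appears consistently in three places (section 7.1.2.9 and the SD and PD cells of Table 6), and Table 6 sets it next to the 5 mm rule. It may therefore be deliberate. The list in section 7.1.2.9 is not exhaustive either, since it omits the difference in non-target handling that Table 6 shows. This stands in part: intent cannot be proved. But the plan nowhere explains a threshold that runs against the direction of the differences it does list.

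Confirmation may delay or cancel a small-growth irPD. That holds under section 7.1.2.9, which sets no time limit. The Table 6 footnote requires confirmation only for a first irPD up to the 9-week scan. On-treatment imaging starts at Cycle 2 Day 1, about Week 9, and repeats every 8 weeks (7.1.4.2). Regrowth from a nadir seen at Week 9 is therefore first visible at about Week 17, outside the footnote. Confirmation also does not remove true growth of 2 to 4 mm.

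Several stronger readings are tempting, and the documents do not support them:

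- *The problem falls mainly on the best responders.* This is not shown. Small baseline disease is exposed without any response, and the responder share depends entirely on assumed inputs.
- *irRECIST generally declares progression before RECIST 1.1.* This needs growth of at least 20% but under 5 mm at a scan, no new lesion and no unequivocal non-target progression. Growth of 5 mm or more within one interval from such a nadir meets both size rules together.
- *Deep responders lose their best response.* Section 7.1.2.12.2 blocks only a subsequent one. An irPR or irCR already recorded stays.
- *These changes are below what the scan can resolve, because "Spiral CT scan should be performed using a 5 mm contiguous reconstruction algorithm".* Section 7.1.2.5 ties slice thickness to minimum lesion diameter, not to the smallest detectable change in a diameter, and MRI is also allowed.

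**Conclusion.** The gap is certain from the text. For nadir sums under 25 mm, with no new lesion and no unequivocal non-target progression, irPD is met by less growth than RECIST 1.1 PD, with a shortfall of 5 − 0.20n mm. Deep responders and subjects with small baseline disease are both exposed. The effect is on irRECIST PFS and duration of response, and on irBOR only through loss of a later response.

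The practical size is modest. The 0.3% to 8% of subjects and the false-crossing chances rest on assumed inputs, and the single-scan chances fall where confirmation applies. RECIST 1.1 results are untouched, the same rule applies in every arm, and the plan itself says that treatment comparisons may lack power. The point is still worth correcting, because irRECIST response and PFS stand in a Part B primary objective, the arms are small and the correction is cheap.

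**What to change.** For deriving the irRECIST endpoints:

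- Add *and an absolute increase of at least 5 mm* to irPD in section 7.1.2.9 and to the irRECIST PD cell of Table 6.
- Change the irRECIST SD cell of Table 6 to match, so that growth of at least 20% but under 5 mm is not PD. If only the PD texts were edited, such growth would be neither SD nor PD in that table.

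Both size thresholds are then max(1.2n, n + 5), and the gap is zero at every nadir. The criteria will still differ on new lesions, confirmation, non-target lesions and the Week 9 rule, so the amended text should not claim that only two differences remain. If the bare 20% is intended, the plan should say so and give the reason.

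The cost is a phrase in two places and one aligned cell, with no new data. The downside is that irPD is called slightly later for very small sums.

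Separately, section 7.1.2.9 and the Table 6 footnote must be reconciled on when irPD needs confirmation.
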